3.2.2 Central laboratory

The overall objective of central testing of stored specimens is to understand the impact of baseline serology, as assessed by the POC tests, on outcomes of relevance for the TICO trial. The **primary objective** is to test for an association between the POC test result on stored baseline specimens and the primary efficacy outcome in TICO on a subset of specimens from TICO participants for whom the GenScript assay has result has already been determined. Secondary objectives are as follows:

1. Test for an association between each POC test result on stored baseline specimens and efficacy/safety outcomes in TICO in a case-control design.
2. Compare the POC test results to the GenScript results and other antibody test results such as those from Bio-Rad and Quanterix that have already been obtained for these stored specimens.
3. Select a threshold for the quantitative LumiraDX result to optimize the association between the dichotomized assay result and safety and efficacy outcomes using the stored specimens.
4. Compare the 2 POC platforms to each other and the GenScript result using locally (at each site) and centrally determined POC results.
5. Examine associations between these antibody assays and antigen assays which have already been obtained for the stored specimens.
6. Determine the effect of vaccination and other participant characteristics on the antibody test results.

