3.4.1 Inclusion criteria

1. Age ≥ 18 years.
2. Informed consent by the patient or the patient's legally authorized representative (LAR) for up to 4 fingersticks for POC testing and a blood draw for stored blood samples.
3. SARS-CoV-2 infection, documented by a nucleic acid test (NAT) or equivalent testing within 3 days prior to consent OR documented by NAT or equivalent testing more than 3 days prior to consent AND progressive disease suggestive of ongoing SARS-CoV-2 infection per the responsible investigator. (For non-NAT tests, only

those deemed with equivalent specificity to NAT by the protocol team will be allowed. A central list of allowed non-NAT tests is maintained for TICO and that list will also be used for this protocol.)

4. Duration of symptoms attributable to COVID-19 ≤ 12 days per the responsible investigator.
5. Requiring admission for inpatient hospital acute medical care for clinical manifestations of COVID-19, per the responsible investigator, and NOT for purely public health or quarantine purposes.

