3.4.2 Exclusion criteria

1. Prior receipt of SARS-CoV-2 hIVIG, convalescent plasma from a person who recovered from COVID-19, or SARS-CoV-2 nMAb within 6 months of the blood draws for testing as part of this protocol.
2. Disease severity beyond that of stratum 1 in the TICO trial.

This includes the following conditions:

- a. stroke
- b. meningitis
- c. encephalitis
- d. myelitis
- e. myocardial infarction
- f. myocarditis
- g. pericarditis
- h. symptomatic congestive heart failure (CHF; New York Heart Association [NYHA] class III-IV)
- i. arterial or deep venous thrombosis or pulmonary embolism

Or current requirement for any of the following:

- a. high-flow supplemental oxygen
- b. non-invasive ventilation
- c. invasive mechanical ventilation
- d. extracorporeal membrane oxygenation
- e. mechanical circulatory support
- f. vasopressor therapy
- g. commencement of renal replacement therapy at this admission (i.e., not patients on chronic renal replacement therapy).

3. In the opinion of the responsible investigator, any condition for which, participation would not be in the best interest of the participant or that could limit protocol specified assessments.

A blood specimen for storage is required for participation in the study.

These eligibility requirements are nearly identical to those used in the TICO trial from which specimens will be used for the case-control study. One major difference is that TICO participants must agree to not participate in other COVID-19 treatment trials until after Day 5 (this is clearly not relevant for this protocol). The exclusion criteria here are more restrictive than those in the TICO trial. This is so participants in this protocol are comparable to those who enrolled in the TICO trials from whom specimens will be used for the case-control study. Those trials had more restrictive exclusion criteria than listed in the TICO protocol at the request of the FDA and match the exclusion criteria listed here. This will facilitate interpretation of analyses that use specimens from the field test and from the previously conducted trials. Eligibility criteria were also selected to be similar to those in the TICO trial to ensure these results are relevant for

future trials in hospitalized patients conducted by INSIGHT and aligned networks for which eligibility criteria are likely to be similar to TICO.

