3.5 Data and Blood Collection Plan

After providing written informed consent, a CRF will be completed for each participant and blood will be collected by up to 4 fingersticks and by a venous blood draw of 9 mL (in an EDTA collection tube for aliquoting plasma after centrifugation into 4 2 mL cryovials, each with about 1 mL of plasma). The blood from the fingersticks will be used to conduct the POC tests and the plasma cryovials will be stored locally in a -70°/-80° freezer until they can be shipped to the central biorepository. The CRF will capture the outcome of the POC tests, the length of time from the start of the assay to recording the test outcome, and selected data collected on the TICO Screening and Baseline and Randomization forms. This will include

1. Participation in other INSIGHT studies.
2. Demographics.
3. Date of onset of COVID-19 symptoms.
4. Severity of COVID-19.
5. Oxygen requirements.
6. History of chronic comorbidities.
7. SARS-CoV-2 vaccination information.
8. Targeted concomitant medications.
9. Height and weight.

Two fingerstick samples of blood will be obtained, one for each POC test. The plasma samples collected will be used for determination of antibody and antigen levels, and central laboratory determination of the two POC tests.

All study procedures will be performed by study personnel. Training materials and the consent document will clearly state that the results of the POC tests are not to be used for patient management and so should not be shared with the patient or care giver. All study procedures must be performed within 24 hours of completing the written informed consent.

Information will be collected from site staff about ease of use of each platform.

4 Data Analysis

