4.2 Local versus Central POC Test Result Comparison

The primary analysis will test if the odds ratio for the association is 1 using McNemar's chi-square test with a significance level of 0.05. Samples for which either test result is missing will be excluded from this analysis. This test will be supplemented by a 95% CI for the difference in the probability of testing positive. Site level effects will be estimated by using generalized estimating equations for Bernoulli outcomes using a logistic link with pairs of results modelled as

being correlated (the test outcome is the binary outcome). This model will include fixed effects for the test type (i.e., local or central) and site. Sites may be grouped based on geography or ICC membership to improve the precision of site level estimates and the interaction between site and test type will be investigated. Subgroups based on age, existence of an immunocompromising condition and vaccination status will be investigated (provided enough individuals with an immunocompromising condition enroll). These subgroup analyses will test for an interaction between group membership and test type. This analysis will be used for both POC tests, and there will not be an adjustment for the conduct of the 2 sets of analyses.

In addition to the primary analysis, associations between test results and participant characteristics will be investigated. These characteristics include age, sex, existence of an immunocompromising condition and vaccination status.

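### The plan sets out to determine the effect of vaccination on antibody results, but its visible text neither records nor adjusts for earlier SARS-CoV-2 infection, so that association may be confounded

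*Combined protocol and SAP*

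**What the plan says.** **Objective.** Section 3.2.2, secondary objective 6: "Determine the effect of vaccination and other participant characteristics on the antibody test results".

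**Analysis.** Vaccination enters the analysis plan in section 4.2. One use is a subgroup analysis (age, immunocompromise, vaccination) that tests for an interaction with test type. The other is a set of associations between test results and participant characteristics: "These characteristics include age, sex, existence of an immunocompromising condition and vaccination status". Section 4.3 carries the subgroup work over to the comparisons with GenScript. No adjustment set is stated for the vaccination association.

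**Eligibility.** Section 3.4.1 limits the current illness only: "Duration of symptoms attributable to COVID-19 ≤ 12 days per the responsible investigator". The nearest exclusion in section 3.4.2 concerns passive antibody products: "Prior receipt of SARS-CoV-2 hIVIG, convalescent plasma from a person who recovered from COVID-19, or SARS-CoV-2 nMAb within 6 months of the blood draws". Neither list mentions an earlier infection.

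**Data collected.** Besides the point-of-care (POC) results and timings, section 3.5 says the CRF takes "selected data collected on the TICO Screening and Baseline and Randomization forms" and lists nine items. One is "SARS-CoV-2 vaccination information"; others are the symptom-onset date and chronic comorbidities. Earlier infection is not listed. The TICO forms themselves are not in the documents.

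**The concern.** Objective 6 is worded as an effect, while section 4.2 delivers associations with no adjustment set. An infection before the current episode is a plausible alternative source of the outcome. All three assays respond to spike-directed antibody: LumiraDX to the receptor binding domain and S1, RightSign to the receptor binding domain, and GenScript to blocking of that domain (sections 2.1 and 2.3). The protocol's own Tables 2 to 4 show that infection alone makes almost everyone positive at 15 or more days after a positive PCR.

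Under the visible plan, a previously infected, unvaccinated participant joins the unvaccinated reference group with nothing to mark them out. If such people are more or less common there than among the vaccinated, part of the difference reported as vaccination reflects earlier infection. Without the variable, the sponsor could not tell whether the bias is negligible or material, or which way it runs. The results at stake are the vaccination association and, possibly, the vaccination-by-test-type interaction.

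**Working it through.** The documents state no figure for the vaccination contrast, so there is none to reproduce. The calculation below only illustrates size.

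**Inputs**
- Positivity without earlier infection: 46%, borrowed from the GenScript result in 320 TICO placebo participants (section 2.2).
- Positivity with earlier infection: 95%, borrowed from the rows for 15 or more days after PCR. These are RightSign IgM 150/158 = 95%, RightSign IgG 152/158 = 96% and LumiraDX 49/49 = 100%. Persistence to a later admission is assumed.
- Share with earlier infection, *s*, by vaccination group: assumed; the documents give nothing.
- Sample size 375 (section 3.3), assumed half vaccinated, so 187.5 per group.
- True vaccination effect: none.

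**Formula.** Group positivity = *s* × 0.95 + (1 − *s*) × 0.46.
- *s* = 5%: 0.0475 + 0.4370 = 0.4845
- *s* = 10%: 0.095 + 0.414 = 0.509
- *s* = 20%: 0.190 + 0.368 = 0.558
- *s* = 30%: 0.285 + 0.322 = 0.607

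**Crude contrast when the true effect is nil**

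| Earlier infection, vaccinated v unvaccinated | Difference | Odds ratio |
|---|---|---|
| 5% v 10% | −0.025 | 0.91 |
| 5% v 20% | −0.074 | 0.74 |
| 5% v 30% | −0.123 | 0.61 |
| 10% v 10% | 0 | 1.00 |
| 20% v 5% | +0.074 | 1.34 |

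Example for 5% v 20%: (0.4845/0.5155) ÷ (0.558/0.442) = 0.940 ÷ 1.262 = 0.74.

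**Against sampling error.** The standard error of the difference is √(0.46 × 0.54 × 2/187.5) = 0.051. The biases in the first three rows are therefore about 0.5, 1.4 and 2.4 standard errors. With no true effect, a two-sided 5% test would reject about 30% of the time at 5% v 20% and about 67% at 5% v 30%.

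**Sensitivity to the 95%.** If positivity after earlier infection is 80%, the odds ratios move closer to 1: 0.93 (5% v 10%), 0.82 (5% v 20%) and 1.23 (20% v 5%).

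**The case against.** **The bias is conditional.** A reader might infer that the vaccination contrast is confounded. That requires earlier infection to differ by vaccination status among these hospitalized participants, and the documents give no data on it. This stands: the right word is *may*.

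**Equal shares do not bias the contrast.** A reader might infer that mixing previously infected people into both groups dilutes the estimate and so biases it. Suppose vaccination raised positivity from 46% to 75% (29 points) in people without earlier infection, did nothing in those with it, and 20% of each group had an earlier infection. The true average effect is 0.8 × 29 + 0.2 × 0 = 23 points. The crude difference is (0.8 × 75 + 0.2 × 95) − 55.8 = 79.0 − 55.8 = 23 points. That is the correct answer for the mixed population; the 29 points belong to a different one.

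**No reversal is shown.** Under the same assumed effect with 5% v 30% earlier infection, the crude difference is still 76.0 − 60.7 = 15 points in the right direction. In the null scenarios there is no true direction to reverse.

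**Repair is not ruled out.** Because there is a single visit, a reader might infer that the gap is permanent. The Protocol Summary says sites can match identifiers to participants, and section 6 keeps plasma for further study. Record review is therefore possible in principle. It would miss undocumented infections, and since every participant is currently infected, later serology may not separate an earlier infection from the present one.

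**The inputs fit loosely.** The 46% and 95% come from different assays. Section 3.4.2 says the exclusions of the source TICO trials match those here, so the 46% may already include previously infected people. The shares are invented.

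**The item may exist.** The CRF list is introduced by wording that need not be exhaustive, and the TICO forms cannot be seen. Even so, a CRF item alone would not put earlier infection into the analyses of section 4.2.

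**Conclusion.** The omission is real in the visible text, and it bears on a stated objective. The vaccination association may be confounded. If vaccination truly had no effect, the crude odds ratio would run from about 0.91 to 0.61 for 5% v 10% to 30% earlier infection, would exceed 1 (1.34 at 20% v 5%) if the imbalance ran the other way, and would be 1.0 with equal shares. These figures rest on assumed shares and on borrowed 46% and 95% positivity. They show that the bias could range from negligible to more than two standard errors; they do not estimate it.

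The reach is limited. A reader might infer that the local-versus-central and POC-versus-GenScript comparisons are also compromised. They are paired within person, so earlier infection cannot confound their main contrasts. It could modify the vaccination-by-test-type interaction, for which no size has been worked out. No primary objective or sample-size figure depends on this. It is a low-cost improvement to a secondary objective.

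**What to change.** **Section 3.5.** Add one CRF item: SARS-CoV-2 infection before the current episode (yes / no / unknown), whether documented or self-reported, and the date of the most recent one. For participants already enrolled, complete it from site records where available and otherwise code it unknown. If the TICO forms already carry such an item, name it in the list.

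**Section 4.2, and through it 4.3.** Add earlier infection to the named characteristics. Estimate the vaccination association adjusted for it, and repeat the analysis in participants with no known earlier infection.

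**If the item cannot be added,** reword objective 6 as an unadjusted association and state the limitation.

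**Cost.** One question and one covariate; no extra visit, blood or participants. Retrospective completion needs site time and any consent or ethics approval that applies. Undocumented infections will leave residual confounding, and the analysis must carry an unknown category.

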3.3 Sample Size and Statistical Considerations

3.3.1 Local versus central POC test result

The power for comparisons of results from paired qualitative tests on specimens was assessed using Schlesselman's formula for the power of McNemar's chi-square test¹⁰. This requires specification of the odds ratio and the probability of 1 test being positive when the other is negative (denoted p_{01} in the table). Table 1 shows the power as it depends on these 2 parameters with a sample size of 375. By taking the odds ratio to be greater than 1 we are assuming that p_{01} is the smaller of the 2 probabilities of 1 test being positive while the other is negative. For example, $p_{01}=0.01$ and an odds ratio of 2.2 implies that the 2 probabilities that one test is positive while the other is negative are 0.01 and 0.022, and the probability that the 2 tests agree is 96.8%. As can be seen in Table 5, with a sample size of 375 the power of the test is low in this scenario (0.24), but this is fairly strong agreement across the assays. As can be seen from the same table, the test will have over 80% power if $p_{01}=0.03$ and the odds ratio is at least 2.6. This corresponds to the discordance probabilities of 0.03 and 0.078 and the corresponding probability that the 2 tests agree is 89.2%. With this configuration of probabilities for test agreement the standard error for the difference in the probability that the 2 tests are positive is 0.023. There is currently no data available for this comparison.

| Odds ratio | $p_{01}=0.01$ | $p_{01}=0.03$ | $p_{01}=0.05$ |
|------------|---------------|---------------|---------------|
| 2.0 | 0.19 | 0.49 | 0.72 |
| 2.1 | 0.21 | 0.56 | 0.79 |
| 2.2 | 0.24 | 0.62 | 0.85 |
| 2.3 | 0.27 | 0.68 | 0.89 |
| 2.4 | 0.30 | 0.74 | 0.93 |
| 2.5 | 0.33 | 0.79 | 0.95 |
| 2.6 | 0.36 | 0.83 | 0.97 |

Table 5: The power of McNemar's chi-square test for testing the agreement of 2 assays as it depends on the odds ratio and the smaller of the 2 probabilities for test discordance. This assumes the sample size is 375.

3.3.2 Local and central POC test result versus GenScript cPass assay result

Sample size considerations for these comparisons are similar to those from the previous section, but we do have data from 302 participants on the relationship between the central POC test using the RightSign platform and the GenScript assay using stored specimens for both assays. The association depends on which isotype is measured with the RightSign assay: there is evidence that the odds ratio is different from 1 for IgM (odds ratio 7.5, $p<0.001$) but not for IgG (odds ratio 1.1, $p=0.82$). These preliminary data indicate that 375 samples obtained as part of the field test will provide more than adequate power for detecting a difference for the GenScript assay and RightSign IgM assay and very low power for detecting a difference between the GenScript assay and the RightSign IgG assay due to the high degree of association between the latter pair of assays.

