The primary objective of the field test is to test for an association between the outcome of the locally obtained POC test and the centrally obtained result from the GenScript assay on a blood sample obtained at the same time as the sample for the POC tests.

The primary objective of the nested case-control study is to test for an association between the POC test result on stored baseline specimens and the primary efficacy outcome in TICO on a subset of specimens from TICO participants for whom the GenScript assay result has already been determined. Since conducting POC assays on large numbers of stored specimens is time consuming (since each assay takes 10-20 minutes and

each individual specimen must be analysed), a case-control design will be utilized. The case definition is death or time to sustained recovery that exceeds 28 days. To maximize the difference between cases and controls, controls are defined as those with a time to sustained recovery of no more than 16 days. With these definitions there are 68 cases and 77 controls for a total sample size of 145. Of these participants, 104 experienced a sustained recovery (the primary outcome in TICO) and 20 died.

DURATION

Participants in the cross-sectional study will be completed with the study within 24 hours of consent. Actual participation will just involve the consent process, 2 POC tests, and completion of a case report form (CRF) and a blood draw, thus we expect participation to last no more than a few hours.

SAMPLE SIZE

Sample size for the cross-sectional study is targeted at 375. With this sample size the study will have 83% power for detecting a difference in the probability of a positive test between 2 assays when the odds ratio for the 2 assays is 2.6 and the smaller of the 2 probabilities of test discordance is 3%.

The sample size for the nested case-control study is 145. Analysis of the case-control population using the GenScript assay detected a sub-hazard ratio of 1.91. With a sub-hazard ratio of 1.91, 104 events provide 90% power for rejecting the null hypothesis that the sub-hazard ratio is 1 and this number of events provides 80% power for a sub-hazard ratio of 1.75.

POPULATION

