4.3 Local and Central POC Test Result versus GenScript cPass Assay

The GenScript assay will also be conducted on the specimens at the central laboratory. The locally and centrally determined POC results will be compared to the GenScript result using McNemar's chi-square test and will be supplemented by 95% CIs for the difference in the probability of testing positive. Investigation of site effects and test performance in subgroups will be pursued as described in Section 4.2.

4.4 Association of POC Test Results with TICO Outcomes: A Nested Case-Control Study of Completed TICO Trials

TICO specimens selected for the case-control study will be shipped from the repository at Advanced Biomedical Labs LLC to the central laboratory for analysis. The Fine-Grey approach to competing risk regression will be used to test for an association between the POC test result and time to sustained recovery while controlling for the parent sub-study effect. A significance level of 0.05 will be used to test the null hypothesis that the regression coefficient associated with the presence of antibodies at baseline is zero. The association between baseline POC test results and time to death will be investigated using Cox models stratified by parent sub-study. The association between baseline POC test results and the primary safety composite at days 5, 28 and 90 will be investigated using logistic regression models that control for parent sub-study.

Finally, data will be pooled from the field test and the stored specimens for all qualitative assays conducted to test for differences. This would include the local POC, central POC, and GenScript results from the field test, the GenScript result for the stored specimens and the POC results for the stored specimens. This analysis will use generalized estimating equations for binary outcomes with effects for the type of assay (3 values), if the assay was conducted locally or centrally, and in which protocol/sub-study the participant enrolled. The association due to the specimen coming from the same person will be accounted for by including this information as a clustering effect in the model. Tests for differences in the assays will be based on the Wald test for the regression coefficients for the assays. No multiplicity adjustment will be made for these tests.

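### Section 3.3.2 attributes low power for RightSign IgG v GenScript to high association, but a McNemar-type odds ratio near 1 shows only similar positivity, and Sections 4.2-4.3 give no rule for reading a non-significant result

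*Combined protocol and SAP*

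**What the plan says.** Section 3.3.2 uses preliminary data from 302 participants with stored specimens. For RightSign IgM against GenScript it reports an odds ratio of 7.5 (p<0.001). For RightSign IgG it reports 1.1 (p=0.82). From the second result it concludes that the field test will have "very low power for detecting a difference between the GenScript assay and the RightSign IgG assay due to the high degree of association". It prints no 2x2 table, percent agreement, kappa or confidence interval.

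The analysis sections use the same tool:
- Section 4.2 (local v central POC) tests whether an odds ratio for association equals 1, "using McNemar's chi-square test with a significance level of 0.05", and adds a 95% CI for the difference in positivity.
- Section 4.3 compares local and central POC results with GenScript "using McNemar's chi-square test and will be supplemented by 95% CIs for the difference in the probability of testing positive".
- Section 3.3.1 captions Table 5 as "The power of McNemar's chi-square test for testing the agreement of 2 assays".

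Section 3.2.1 states the primary field-test objective as testing for an association between the local POC result and GenScript. The overall aim is to learn whether a POC test can identify people who lack antibodies. No section sets a margin, an agreement target, or a rule for reading a non-significant test.

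**The concern.** McNemar's test compares the two discordant cells of a paired 2x2 table. It asks whether the two assays are positive equally often. It ignores the concordant cells, so it cannot say how often the assays give the same answer for the same person. Two assays can be positive at the same rate and still disagree often.

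This matters for the study's aim. Identifying antibody-negative patients depends on person-level agreement, and Section 2.1 notes that false negatives are the main worry if treating seropositive patients is a safety concern. False negatives that are offset by false positives leave McNemar's test unmoved. Absence of a difference is also the favourable result here, so the plan should say what a non-significant test does and does not show.

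**Working it through.** **Inputs.** n=375 for the field test ("Sample size for the cross-sectional study is targeted at 375"). Alpha is 0.05 (Section 4.2), taken as two-sided. Power "was assessed using Schlesselman's formula for the power of McNemar's chi-square test" (Section 3.3.1). Preliminary IgG result: odds ratio 1.1, p=0.82, 302 participants (Section 3.3.2).

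**1. Reproduce the plan's power.** Let m = n·p01·(1+OR) be the expected number of discordant pairs and P = OR/(1+OR). Then power = Φ[(√m·|P−0.5| − 1.96/2)/√(P(1−P))]. For OR 2.6 and p01=0.03: m = 375×0.03×3.6 = 40.5, P = 0.722, power = Φ[(6.364×0.222 − 0.98)/0.448] = 0.834. The plan prints 0.83. All 21 cells of Table 5 reproduce.

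**2. Does high association explain the low power at OR 1.1?** The same formula with OR 1.1 (P = 0.524), n=375:

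| p01 | Agreement (1 − 2.1·p01) | Power |
|---|---|---|
| 0.01 | 97.9% | 3% |
| 0.03 | 93.7% | 4% |
| 0.10 | 79% | 6% |
| 0.20 | 58% | 9% |

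Counting both rejection tails gives 5% to 9% over the same range. Now hold agreement at the design value of 89.2%: power is 83% at OR 2.6 and about 5% at OR 1.1. The near-balance of the discordant cells drives the result.

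**3. What agreement do OR 1.1 and p=0.82 imply?** Assume that 1.1 is the raw ratio b/c of discordant counts, that there are 302 complete pairs, and that p is unadjusted. For the uncorrected test, p=0.82 needs (b−c)²/(b+c) ≈ 0.052.
- b−c=1 gives b+c ≈ 19, so 10/9 (ratio 1.11, p=0.8185).
- b−c=2 gives b+c ≈ 77, so 38/36 to 41/39 (74 to 80 pairs).
- b−c=3 gives b+c ≈ 174, a ratio near 1.03, which would not print as 1.1.

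The continuity-corrected and exact tests admit only the second group (73 to 81 pairs, for example 40/37). Mid-p admits 10/9 and also 72 to 80 pairs. Agreement is therefore (302−19)/302 = 93.7%, or between (302−81)/302 = 73.2% and (302−73)/302 = 75.8% (76.2% with 72 pairs).

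**4. What each solution means.** The CI for the difference is (b−c)/302 ± 1.96·√{[(b+c)/302 − ((b−c)/302)²]/302}.
- 10/9: −2.5 to +3.2 points. The CI for the odds ratio is 0.45 to 2.73, which includes the design value of 2.6.
- 40/37: −4.7 to +6.7 points. Either 37 or 40 of the 302 would be GenScript-positive and IgG-negative, against 9 or 10 under the first solution.

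If both assays were 46% positive (an assumption, from the GenScript figure for 320 placebo participants in Section 2.2), chance agreement is 0.46² + 0.54² = 0.503. Kappa is then (0.937−0.503)/0.497 = 0.87, or (0.745−0.503)/0.497 = 0.49 for 40/37.

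**5. How often would a real difference give a non-significant test?** From Table 5 itself: p01=0.05 with OR 2.0 is a 5-point shift and is missed 28% of the time (power 0.72). p01=0.03 with OR 2.0 is a 3-point shift, missed 51% (power 0.49). Fifteen of the 21 cells have power below 80%. At a fixed absolute shift, more discordance lowers power: simulated power for a 5-point shift (an illustrative size, not in the documents) is 85%, 71%, 59% and 49% at 11%, 15%, 20% and 25% discordance. At a fixed odds ratio the direction reverses: in Table 5 at OR 2.0, power rises from 0.19 to 0.49 to 0.72 as p01 rises.

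**The case against.** Several points on the other side stand.

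- **No claim of equivalence.** A reader might infer that the plan will treat non-significance as proof that the assays are interchangeable. No section says so. Section 3.3.2 openly discloses very low power, and Sections 4.2 and 4.3 plan 95% CIs that would show imprecision.
- **Section 3.3.1 does not make this error.** A reader might also cite its remark that "the power of the test is low in this scenario (0.24), but this is fairly strong agreement across the assays". There, agreement is computed correctly from assumed discordance (1 − 0.01 − 0.022 = 96.8%) and kept apart from power.
- **The assays may agree well.** The 10/9 split gives 93.7% agreement. The authors hold the data and may have grounds that they did not print.
- **McNemar is inferred.** Section 3.3.2 does not name the test behind 1.1. It says only that considerations resemble those of the preceding section. The agreement ranges depend on that reading. If 1.1 were an ordinary cross-product odds ratio, however, it would mean almost no association, so the sentence fails on either reading.
- **Agreement does affect power in general.** At OR 2.6, power falls from 0.97 to 0.36 as p01 falls from 0.05 to 0.01. The explanation in Section 3.3.2 is not baseless, but it does not identify what matters at OR 1.1.
- **IgG alone is not the binary RightSign result.** Section 2.3.2 defines RightSign as positive if either isotype is positive, so the preliminary IgG figure does not by itself decide a field comparison.

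What remains is that the printed figures cannot support the stated reason, and that the plan labels a test of positivity as one of association or agreement without saying how to read a null result.

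**Conclusion.** The point holds as a matter of interpretation and reporting. The figures in Section 3.3.2 show no detectable difference in positivity between RightSign IgG and GenScript. They do not show a high degree of association: under the assumptions in step 3 they fit about 94% agreement or about 73-76%. Power at OR 1.1 with 375 pairs is below about 10% anywhere from 58% to 98% agreement. The same conflation appears in Section 4.2, in Section 4.3 read with the primary objective, and in the Table 5 caption.

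The documents do not support a claim that the assays agree poorly, nor that the sponsor intends to declare equivalence from a non-significant test. That risk is left open and is partly mitigated by the planned CIs. Those CIs concern positivity only and come without a reading rule.

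**What to change.** 1. **Section 3.3.2.** Replace the clause about association with: *because the observed odds ratio was near 1 (similar positivity), which does not by itself show agreement*. Name the test used. Print the 2x2 counts for IgG, IgM and, if available, the IgM-or-IgG definition of Section 2.3.2.
2. **Sections 4.2 and 4.3.** State that a non-significant McNemar test is not evidence of agreement. Rest conclusions on similar positivity on the planned 95% CI. If similarity is to be claimed, judge the CI against a margin that the sponsor chooses and justifies before results are seen. Report agreement from the same 2x2 tables as positive and negative percent agreement, or kappa, with 95% CIs. A positivity margin alone would not measure agreement.
3. **Table 5 caption.** Describe the test as *testing the difference in positivity of 2 assays*.

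For choosing a margin, the expected 95% CI half-width at n=375 and OR 1.1 is about 2.5 points at 6.3% discordance, 3.3 at 10.8%, 4.5 at 20% and 5.5 at 30%. The standard error of 0.023 in Section 3.3.1 should be reconciled first: with discordance 0.03 and 0.078, √[(0.108 − 0.048²)/375] = 0.017.

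The cost is wording, counts that the sponsor should already hold, and a few extra summary statistics. No data collection changes. The downside is that some comparisons will have to be reported as inconclusive.
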